8.3. Overall Response Rate

A patient's best overall response is defined as the best investigator-assessed RECIST response to treatment category recorded since the start of the treatment. The hierarchy of response ratings, best to worst, is CR, PR, SD, PD, followed by NE. The numbers and percentages of subjects achieving each of these response categories will be summarized within treatment group.

The ORR, defined as the proportion of patients achieving a CR or PR, and its 95% confidence interval will be computed within treatment group. The p-value for equality between treatment groups will be calculated for the two groups using a logistic regression model including treatment, platinum choice (cisplatin versus carboplatin) and prior treatment modality (WBRT or PCI) as categorical independent variables. Patients without any post-baseline tumor assessments will be classified among those never achieving a CR or PR.

The impact of the biomarkers Notch3, Hes1, Hey2, Hey1 and Hes6 on ORR will be evaluated with a logistic regression model with treatment, biomarker and treatment-by-biomarker interaction included in the model as independent variables. A separate logistic regression model will be used for each biomarker.

8.4. Duration of Response

Analyses of DOR include only patients who achieved a CR or PR; patients failing to achieve a CR or PR during the study are omitted from analyses of DOR. If the number of patients achieving a CR or PR is not sufficient to produce meaningful KM curves, then the planned analyses for DOR may be abandoned.

DOR is defined as the number of days from the first CR or PR until the first occurrence of death or disease progression based on investigator assessments of tumor response per the RECIST criteria. Progressions that are not determined from on study tumor assessments as well as deaths occurring more than 49 days from the last on-study tumor assessment are not treated as progression events. Subjects achieving a CR/PR but without a subsequent progression event will be censored at their last on study tumor assessment.

In addition two special cases will be handled in a manner consistent with the above rules as follows:

1. Patients whose next tumor assessment (following the first CR/PR) is >91 days after the first CR/PR will be censored on the date of the first CR/PR with a DOR of 1 day.
2. Patients who never had an on study tumor assessment after the first CR/PR and who did not die within 49 days (the scheduled time between tumor assessments plus 7 days) after the first CR/PR will be censored on the date of first CR/PR with a DOR of 1 day.

The KM method will be used to estimate the proportions of CR/PR patients over time who have not experienced RECIST disease progression and the median DOR. KM curves will be plotted and 95% confidence intervals for median DOR will also be calculated for each treatment arm. The HR, its 95% confidence interval and the p-value for testing the statistical significance of the

treatment effect will be generated using a Cox PH model with main effects for treatment, platinum choice (cisplatin versus carboplatin) and prior treatment modality (WBRT or PCI).

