6.1. Analysis Populations

The following five groups of study patients will be used for statistical analyses.

1. The ITT patient population includes all patients randomized to receive study drug regardless of whether they actually received study drug and regardless of whether evidence is found indicating they failed to meet study inclusion/exclusion criteria or had other protocol violations. When the ITT patient population is analyzed, patients are grouped according to

their randomized treatment regardless of actual treatment received. The ITT patient population is the analysis population for demographics and baseline characteristics and for all statistical inference and primary tests of hypotheses related to efficacy endpoints.

2. The safety patient population is the subset of ITT patients who received at least one dose of study drug. When the safety patient population is analyzed, patients are grouped according to actual treatment received. Tarextumab is considered a patient's "treatment received" in the safety patient population if the patient received at least one dose of tarextumab (complete or incomplete dose) any time during the study. The safety patient population is the analysis population for all analyses of safety data.
3. The per-protocol (PP) patient population is the subset of safety patients who either (a) have at least one response evaluation on study, or (b) die prior to their first scheduled response evaluation. When the per-protocol patient population is analyzed, patients are grouped according to actual treatment received. The per-protocol population is used for sensitivity (secondary, supportive) analyses of efficacy endpoints.
4. The pharmacokinetic (PK) patient population is comprised of all subjects who received at least one complete dose of tarextumab and have at least one post-dose PK sample.
5. The immunogenicity patient population is comprised of all subjects who had a baseline and one or more follow-up samples obtained for quantifying anti-tarextumab antibody.

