Hey2	xx.x (xx.x)	xx.x (xx.x)	x.xx [x.xx,xx.xx]	x.xx [x.xx,xx.xx]	x.xx [x.xx,xx.xx]	
Hey1	xx.x (xx.x)	xx.x (xx.x)	x.xx [x.xx,xx.xx]	x.xx [x.xx,xx.xx]	x.xx [x.xx,xx.xx]	
Hes6	xx.x (xx.x)	xx.x (xx.x)	x.xx [x.xx,xx.xx]	x.xx [x.xx,xx.xx]	x.xx [x.xx,xx.xx]	

^[1] Coefficients, odds ratio and 95% confidence interval from logistic regression models with effects for treatment, biomarker and treatment-by-biomarker interaction. A separate model was used for each biomarker.

Programmer notes: (a) repeat this table using the per-protocol population

Table 14.2.6.1
Duration of Response
ITT Population

	Placebo (N=xx)	Tarextumab (N=xx)
Number of Subjects with Objective Response (CR or PR)	xx	xx
Total Follow-Up Time (person-years) ^[1]	xxx.x	xxx.x
Number of Responders with Disease Progression or Death	xx (xx.x%)	xx (xx.x%)
Number of Responders who did not Progress or Die (Censored)	xx (xx.x%)	xx (xx.x%)
Hazard ^[2]	0.xx	0.xx
Kaplan-Meier Estimates: Quartiles [95% C.I.] (days)		
25 th Percentile	xxx [xxx,xxx]	xxx [xxx,xxx]
50 th Percentile	xxx [xxx,xxx]	xxx [xxx,xxx]
75 th Percentile	xxx [xxx,xxx]	xxx [xxx,xxx]
Range (Responders who Progressed or Died) (days)	xx.x – xx.x	xx.x – xx.x
Range (All Responders) (days)	xx.x – xx.x	xx.x – xx.x
Hazard Ratio [95% C.I.] ^[3]		x.xx [x.xx,x.xx]
P-value ^[2]		0.xxx

Note: For this table summary, Responders are those subjects who experienced an Objective Response.

Note: Analyses presented in this table include only subjects who achieved a CR or PR. Percentages below the first row are based on subjects who achieved a CR or PR.

Note: Duration of Response = Date of Documentation of Death/Progression – Date of First Partial (PR) or Complete Response (CR) + 1. Responders who had not experienced death or progression by their last contact were censored at the time of their last radiographic response assessment. Responders lacking a radiographic response assessment after first response who do not progress or die have their event time censored on the date of first response with duration of 1 day. For detailed event and censoring rules refer to protocol section 13.5.3 and SAP section 8.4. C.I. = Confidence Interval.

^[1] Sum of all individual follow-up times in days divided by 365.25.

^[2] Number of Subjects with Disease Progression or Death/ Total Follow-up Time (Person-years).

^[3] Hazard ratio, 95% C.I. and p-value from Cox proportional hazards model with main effects for treatment, platinum choice and prior treatment modality.

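### The duration-of-response hazard ratio and p-value are presented as a test of the treatment effect in an ITT table, but they compare only responders, a group formed after randomization that tarextumab may itself change

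*SAP*

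**What the plan says.** Section 8.4 (Duration of Response) restricts the analysis set: "Analyses of DOR include only patients who achieved a CR or PR". Patients who never respond are left out. The clock starts after randomization: "DOR is defined as the number of days from the first CR or PR until the first occurrence of death or disease progression". The section then plans an HR, a 95% confidence interval and "the p-value for testing the statistical significance of the" (the sentence continues) "treatment effect will be generated using a Cox PH model with main effects for treatment, platinum choice", with prior treatment modality as the remaining factor.

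The shell for Table 14.2.6.1 in Appendix B is titled for the ITT population, and a programmer note repeats it for the per-protocol population as Table 14.2.6.2. Its notes say "Analyses presented in this table include only subjects who achieved a CR or PR" and describe the estimates as "Hazard ratio, 95% C.I. and p-value from Cox proportional hazards model with main effects for treatment, platinum choice and prior treatment modality".

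Three other sections bear on this:
- Section 6.1 makes the ITT population the one "for all statistical inference and primary tests of hypotheses related to efficacy endpoints".
- Section 8 lists duration of response (DOR) among the efficacy endpoints.
- Section 5 sets a two-sided 0.05 level for tests unless otherwise noted, and section 8.4 notes nothing else.

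The only qualifier in section 8.4 is that the DOR analyses may be dropped if responders are too few for meaningful Kaplan-Meier curves. Nothing labels the comparison as descriptive or non-randomized.

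**The concern.** A p-value for the treatment effect should rest on groups that differ only by randomized treatment and chance. The two responder groups do so only if tarextumab does not alter who responds. Section 8.3 compares response rates between arms, so the plan itself allows that it may.

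The hypothesis actually tested is that responders under tarextumab and responders under placebo have the same duration. That differs from no treatment effect whenever the drug brings in patients who would not have responded on placebo. Adjusting for platinum choice and prior radiation does not repair this, because the selection runs through each patient's unmeasured tendency to respond.

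At stake is the reading of one HR and p-value in the study report. A ratio above 1 could come from extra, shorter responses with no patient harmed, and a real gain in duration could be masked in the same way.

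**Working it through.** The SAP gives no effect size, power or response rate for DOR, so there is no DOR figure to reproduce. As a check on the method, Schoenfeld's formula at one-sided 0.15 gives power 0.8089 for 91 PFS events at HR 0.67 (Table 1 states 0.8090), and 0.8045 for 98 deaths at HR 0.682 (Table 5 states 0.8047).

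**Inputs from the SAP.** 1:1 allocation; about 135 patients, so about 67 per arm; two-sided 0.05, hence 2.5% in each direction; control PFS hazards per month from Table 3 of 0.1386 (0–5 months), 0.3466 (5–7) and 0.6931 (7–8). For later months 0.1386 is used, the value in the title of Table 2, which that title applies beyond 9 months; here it is applied from month 8. Table 3 itself shows 0.0693 and 0.2310 after month 8, and using either barely changes the results.

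**Assumed, not in the SAP.** Control response 50–60%, the gain in response, the length of added responses, and the correlation between the tendency to respond and PFS.

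**Step 1: direction.** Take control response 60% and a gain of 20 points. Added patients are 0.20/0.80 = 25% of tarextumab responders. Let the usual responders have exponential durations with median 5 months (hazard ln 2/5 = 0.1386) and let the drug change no one's duration. At the start of response, the ratio of the tarextumab responders' hazard to the placebo responders' hazard is 0.75 + 0.25 × (5/m), where m is the added responders' median in months:
- m = 1.5: 0.75 + 0.25 × 3.33 = 1.58
- m = 2.5: 0.75 + 0.25 × 2 = 1.25
- m = 5: 0.75 + 0.25 × 1 = 1.00
- m = 7.5: 0.75 + 0.25 × 0.667 = 0.92

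The ratio then changes as the shorter responses end, so the Cox HR averages over it. Simulation under this model (67 per arm, 4,000 trials, censoring about one third or less) gives:

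| Gain in response | Added responders' median | Responder-only HR | Significant against tarextumab (nominal 2.5%) |
|---|---|---|---|
| 0 | – | 1.00 | 2.5–3% |
| 10 points | 2.5 months | 1.10–1.11 | about 5.4% |
| 10 points | 1.5 months | 1.15–1.18 | about 7.7% |
| 20 points | 2.5 months | 1.17–1.19 | 8–9% |
| 20 points | 1.5 months | 1.27–1.31 | 15–16% |
| 10–20 points | 5 months | about 1.00 | about 2–3% |
| 10–20 points | 7.5 months | 0.88–0.94 | below 2% |

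Ranges cover control response of 50% and 60%. In the last row the distortion favours tarextumab: significant results in its favour occur in about 4–7% of trials.

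**Step 2: size when response tracks progression.** Each patient has a latent tendency to respond, correlated with PFS. PFS follows the hazards above and is identical in both arms. Responders are those above a threshold set by the response rate; response occurs at about 6 weeks; censoring runs at half the event hazard. A Cox model is fitted to time from response among responders.
- No response difference: HR about 1.00, total two-sided rejection about 5%.
- Gain 5–10 points, correlation 0.3–0.5: median HR about 1.03–1.08, total rejection about 5–6%.
- Gain 20–25 points, correlation 0.5–0.7: median HR about 1.1–1.3, wrong-direction rejection about 6–13%.

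**Step 3: masking.** With a true PFS HR of 0.65 and the same correlations of 0.5–0.7, power of the DOR test is about 33–40% when response is 60% in both arms, and about 20–22% when tarextumab raises it to 80%.

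**The case against.** The restriction is disclosed. Section 8.4 states it, the shell repeats it, percentages are based on responders, and the number of responders per arm has its own row. The ITT title mainly separates Table 14.2.6.1 from its per-protocol twin.

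DOR appears in none of the objectives in section 2. It has no power statement or decision rule, and the spending functions in section 5.5 cover PFS and OS only. PFS, response rate and OS are each tested in all randomized patients, so a reader who sees a DOR HR above 1 would also see the response gain and the PFS result. For small gains in response the error rate is close to nominal, and the large distortions need a drug that adds 20–25 points of response without moving PFS.

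All of this stands, and it limits the weight of the point. It does not remove it. Disclosing the subset does not make the p-value a test of the treatment effect, which is what section 8.4 calls it, and it sits badly with section 6.1, which places efficacy inference in the ITT population.

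A reader might go further and infer that a drug which adds responders must look worse on DOR. The documents do not support that. They say nothing on how long added responses last, and the bias vanishes or reverses if these are as long or longer. Nor is the test invalid in every case: with no difference in response it keeps about its 5% level.

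**Conclusion.** The point holds in conditional form. Section 8.4 and Tables 14.2.6.1–14.2.6.2 present as a test of the treatment effect a comparison that randomization does not protect once tarextumab changes who responds. The sign of the bias depends on how long the added responses last.

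Its size runs from negligible (gains of 5–10 points at correlation 0.3–0.5) to a wrong-direction error of roughly two to five times nominal (6/2.5 = 2.4; 13/2.5 = 5.2) for gains of 20–25 points at correlation 0.5–0.7. These figures rest on response rates and correlations that the SAP does not give. No conclusion on PFS, response rate or OS is affected. The point is minor to moderate, and worth correcting because the correction is easy.

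**What to change.** In section 8.4 and the shells for Tables 14.2.6.1 and 14.2.6.2:
- Keep the Kaplan-Meier curves and medians among responders by arm, labelled descriptive.
- Delete the p-value as a test of treatment effect. If the HR and confidence interval are kept, label them descriptive and non-randomized.
- Retitle the tables as responders in the ITT population and responders in the per-protocol population.

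Optionally, if a between-arm comparison is wanted, define one on all randomized patients, such as restricted mean time in response with non-responders counted as zero, to a horizon fixed before unblinding.

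The cost is SAP and shell wording, with no new data, and the loss of one p-value for an endpoint that is not a stated objective. The optional measure adds some programming and a horizon to be chosen.

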8.5. Sites of Progression

Sites of progression will be categorized as stemming from (1) a new lesion or (2) progression of an existing lesion. Treatment-group distributions based on this binomial categorization will be tested using a chi-square test. Then “new lesions” will be further categorized by anatomical site. Patients with new lesions at multiple anatomical locations will be classified as a single category. The resulting multinomial distributions will also be compared across treatment groups using a chi-square test.

8.6. Overall Survival

OS is defined as the number of days from randomization (Day 1) until death. The following rules will be used to define censored observations and censoring times for OS.

1. A patient for whom no death date is reported will have OS censored on the last contact date (defined on page 6). When evaluating the last contact date using the ‘Follow-Up After Discontinuation of Study Treatment’ CRF, both of the ‘date of survival assessment’ (if checked ‘alive’ for ‘subject status’) and the ‘last known survival date’ (if checked ‘alive or ‘lost to follow-up’ for ‘subject status’) will be considered.
2. Patients lacking data after randomization who do not die have their event time censored on the date of randomization with duration of 1 day.
3. All patients alive on the date of the 98th sequential patient death will have their OS censored on the day following the date on which the 98th patient died. All patient deaths will be counted towards the total of 98, independent of which treatment arm the deceased patients were randomized to.

The KM method will be used to estimate survival proportions over time. KM survival curves will be plotted and 95% confidence intervals for median OS will also be calculated for each treatment arm. The HR, its 95% confidence interval and the p-value for testing the statistical significance of the treatment effect will be generated using a Cox PH model with main effects for treatment, platinum choice (cisplatin versus carboplatin) and prior treatment modality (WBRT or PCI).

OS will also be analyzed separately for two subsets of ITT patients defined by platinum choice (cisplatin or carboplatin). In this case, the p-value for testing the statistical significance of the treatment effect will be generated using a Cox PH model with main effects for treatment and prior treatment modality only.

The impact of the biomarkers Notch3, Hes1, Hey2, Hey1 and Hes6 on OS will be evaluated with a Cox PH model with treatment, biomarker and treatment-by-biomarker interaction included in the model as independent variables. A separate Cox PH model will be used for each biomarker.

The planned timing for the primary analysis of OS is stated in section 5.5 above.

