3.1. Blinded Treatment Phase

Subjects who qualify for enrollment into the phase-2 portion of the study will be randomized in a 1:1 ratio to receive study treatment of EP with placebo or EP with tarextumab. The randomization will be balanced on the choice of platinum therapy (cisplatin versus carboplatin) and the prior use of whole brain radiation (WBR) or prophylactic cranial irradiation (PCI). Changing the choice of platinum therapy is not permitted once the subject is randomized. Treatment for each subject will begin on Cycle 1, Day 1 (the first dosing day). Etoposide 100 mg/m² will be given on Days 1, 2 and 3 and cisplatin 75 mg/m² or carboplatin to an AUC of 5 mg/mL/min will be given on Day 1 of every 21-day cycle for 6 cycles. Subjects may remain in the blinded treatment phase to continue one of the chemotherapy drugs if the other is held or discontinued prior to completing 6 cycles of EP and prior to disease progression. For subjects who have study drug held or discontinued for tolerability reasons, EP chemotherapy should continue to the completion of 6 cycles. Subjects may continue study drug if one or both of the chemotherapy drugs is held or discontinued prior to completing 6 cycles of EP and prior to disease progression.

After the completion of 6 cycles of EP, subjects who do not have disease progression and have not had WBR or PCI prior to study entry and are good candidates for PCI according to the

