Analyses 1 and 2 will take place at the last two quarterly safety review meeting of the Data Safety Monitoring Board (DSMB). The estimated numbers of events at these times are presented in Table 1. If the number of events differs from what is presented, then the efficacy and safety boundaries will be recalculated using the spending functions which are footnoted in Table 1.

Overall survival is a secondary endpoint in this study. An analysis of OS will take place at the time of each analysis for PFS as well as at the time that the final analysis of PFS takes place. The final analysis of OS will take place when there are 98 events or 6 months after the final analysis for PFS, whichever occurs first. Table 2 and Figure 1 present enrollment, PFS events and Deaths over time assuming a control hazard of progression beyond 9 months of 0.1386.

[figure not shown]
Table 2. Enrollment, Progressions and Deaths over Time – Control Hazard of Progression of 0.1386 Beyond 9 Months

Study Time (months)	6	12	13	14	15	16	17	18	19	20
Cumulative Enrolment	22	77	85	89	91	105	119	133	134	134
Total PFS Events	5	31	38	43	49	55	62	69	75	80
Total PFS Events-2 [1]	6	35	42	48	54	61	68	76	82	87
Total Deaths	3	19	23	27	32	37	42	49	55	61
Total Deaths-2 [1]	4	22	27	32	37	42	49	56	63	69
Censored PFS (tarextumab)	1	5	6	7	8	9	10	11	12	13
Censored PFS (placebo)	1	4	5	6	7	8	9	9	10	11

Study Time (months)	21	22	23	24	25	26	27	28	29	30
Cumulative Enrolment	134	134	134	134	134	134	134	134	134	134
Total PFS Events	85	90	94	96	97	98	99	99	100	100
Total PFS Events-2 [1]	92	98	101	103	104	104	105	105	105	106
Total Deaths	66	72	77	81	86	91	95	99	102	105
Total Deaths-2 [1]	75	81	86	91	96	100	104	108	111	114
Censored PFS (tarextumab)	14	15	15	16	16	16	16	16	16	17
Censored PFS (placebo)	12	12	13	13	13	13	13	13	13	13

[1] Total PFS Events-2 and Total Deaths-2 refer, respectively, to the expected numbers of progressions and deaths when tarextumab does not prolong progression or death.

Figure 1. Enrollment, Progressions and Deaths over Time – Control Hazard of Progression of 0.1386 Beyond 9 months

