We see from Table 2 that approximately 70% of the 98 deaths required for the final analysis of survival are expected to be observed at the time of the final analysis for PFS. Table 5 presents the power to detect benefit in OS for several HRs assuming that type 1 error is controlled at the 0.15 level and additional analyses take place at approximately 50%, 67% and 83% of full information. These additional analyses will take place at the quarterly DSMB review meetings. If the actual number of events at the review meetings differs from what is presented in the table, the efficacy and safety boundaries will be recalculated using the spending functions footnoted in Table 5.

Table 5. Overall Survival: Power for the Alternative Hypothesis

	Analysis 1	Analysis 2	Analysis 3	Final Analysis
Total Number of Events	49	66	81	98
Z-Statistic (reject the null) [1]	3.889	3.174	2.333	1.036
P-value (1 sided)	0.000050	0.00075	0.0098	0.15
Z statistic (reject the Alt) [2]	-2.1	-1.848	-1.511	-1.082
P-value (1 sided)	0.018	0.032	0.0658	0.139
Cumulative Type 1 Error (1-sided)	1e-04	8e-04	0.0099	0.1501
Cumulative Power				
HR=0.75	0.0020	0.0226	0.1499	0.6511
HR=0.682	0.0054	0.0530	0.2711	0.8047
HR=0.65	0.0086	0.0777	0.3471	0.8637
HR=0.60	0.0178	0.1365	0.4869	0.9324
HR=0.50	0.0717	0.3610	0.7846	0.9918
Cumulative Probability of Stopping for Harm				
Alternative	3e-04	5e-04	9e-04	0.0019
Null	0.0179	0.0381	0.0744	0.1501
HR=1.33 (1/0.75)	0.1372	0.2660	0.4332	0.6470

	Analysis 1	Analysis 2	Analysis 3	Final Analysis
HR=1.47 (1/0.682)	0.2235	0.4037	0.6007	0.8000
HR=2.00 (1/0.50)	0.6278	0.8426	0.9496	0.9911

[1] The boundary for rejecting the null hypothesis for efficacy is obtained from the gamma(-16) alpha spending function.

[2] The boundary for rejecting the null hypothesis for harm is obtained from the gamma(-4) alpha spending function.

With 98 deaths at the final analysis, there is 80% power with 0.15 type 1 error to detect a HR of 0.682. There is a 7.4% chance of stopping early for harm under the null hypothesis, a 43.3% chance of stopping early for harm if the HR=1.33 (1/0.75); a 60.1% chance of stopping early for harm if the HR=1.47 (1/0.682); and a 95.0% chance of stopping early for harm if the HR=2.00 (1/0.5).

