5. GENERAL ANALYSIS CONSIDERATIONS

The statistical analyses will be reported using summary tables, figures and listings (TFLs). Unless otherwise noted, all statistical testing will be two-sided and will be performed at the 0.05 level of significance.

- Continuous variables will be summarized with the number of non-missing values, estimated means, standard deviations, medians, 25th and 75th percentiles, and observed minimum and maximum values.
- Categorical variables will be summarized by counts and by percentages. The percentage of patients within a category will be displayed in parentheses rounded to the nearest tenth of one percent. However, when the number of patients within a category is 0, then the percentage (i.e., 0.0%) will be omitted.
- Time-to-event variables will be summarized by KM estimates of quartiles, observed minimum and maximum values, and the number of censored observations. The hazard will be estimated by the sum of all individual follow-up times in days divided by 365.25.

Any durations of time expressed in months will be reported in proportional “months” according to the formula

$$\text{months} = \frac{365.25}{12} \text{ days.}$$

Summary tables will be presented by treatment group. Individual subject data will be presented in data listings.

The analyses described in this plan are considered *a priori*, in that they have been defined prior to database lock and prior to breaking the treatment blind. If any *a posteriori* analyses (i.e., analyses not included in this SAP) are performed, they will be identified as such in the CSR where the objective and rationale for executing any *a posteriori* analyses will be documented.

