5.4. Subgroup Analyses

Plans for analyses of subgroups based on the presence or absence of anti-tarextumab antibodies are presented in section 11.7 below.

No analyses by baseline characteristics or study center are planned.

Subgroup analyses by baseline Notch3, Hes1, Hey2, Hey1 and Hes6 expression levels are not planned, but the impact these potentially important covariates have on the efficacy of tarextumab will be assessed through statistical modeling (see sections 8.1, 8.3, 8.6 and 8.7).

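### OS is tested separately in the cisplatin and carboplatin subsets with no treatment-by-platinum interaction, so the plan has no valid test of whether the effect differs by platinum

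*SAP*

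**What the plan says.** After the main OS analysis, SAP Section 8.6 adds that "OS will also be analyzed separately for two subsets of ITT patients defined by platinum choice (cisplatin or carboplatin". Each subset gets its own treatment p-value, "using a Cox PH model with main effects for treatment and prior treatment modality only". The shells for Tables 14.2.1.3 and 14.2.1.5 give each subset a hazard ratio with 95% CI, Kaplan-Meier summaries and a p-value row, and both are repeated for the per-protocol population.

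The full-ITT OS model in Section 8.6 has main effects for treatment, platinum choice and prior treatment modality, with no treatment-by-platinum term. The same section gives each of the five biomarkers a treatment-by-biomarker interaction.

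No significance level is set for the subset tests. Section 5 says that, unless otherwise noted, "all statistical testing will be two-sided and will be performed at the 0.05 level of significance". Section 5.5 deals with repeated looks at PFS and OS, not with these subsets. Section 5.4, on subgroup analyses, does not mention the platinum subsets and says "No analyses by baseline characteristics or study center are planned".

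The subsets are also defined in two ways. Section 8.6 uses platinum choice, while the titles and footnotes of the two shells use the platinum actually received.

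**The concern.** Splitting OS by platinum invites the question of whether tarextumab works equally well with both partners. A p-value within each subset answers a different question, namely whether there is evidence of an effect in that subset alone. With fewer than 100 deaths divided in two, each subset has little power. One p-value below 0.05 and one above it is then a common result even when the effect is the same in both. A reader given only that pair could conclude that the drug works with one platinum and not the other, and the plan offers no estimate of the difference to check that conclusion against.

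**Working it through.** **Inputs from the SAP**
- Deaths at the final OS analysis: 98 (Section 4: "The final analysis of OS will take place when there are 98 events").
- Design effect: "there is 80% power with 0.15 type 1 error to detect a HR of 0.682" (Section 4; Table 5 shows the 0.15 as one-sided).
- Allocation 1:1, balanced on platinum choice (Section 3.1).
- Level for the subset tests: two-sided 0.05, the Section 5 default.

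**Assumption.** The SAP does not give the split of deaths by platinum. It is varied here from 50/50 to 90/10.

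**Reproducing the plan's own figure.** With 1:1 allocation, the log-rank or Cox statistic for *d* deaths is approximately normal with mean (√d/2)·|ln HR| and variance 1. For *d* = 98 and HR 0.682, |ln HR| = 0.3827 and the mean is 4.950 × 0.3827 = 1.894. Power at one-sided 0.15 is Φ(1.894 − 1.036) = Φ(0.858) = 0.8045. Table 5 gives 0.8047, so the method matches the plan's.

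**Power in each subset, same HR in both, two-sided 0.05.** The opposite tail is negligible.
- 50/50 (49 and 49 deaths): mean 3.5 × 0.3827 = 1.340; power Φ(1.340 − 1.960) = 0.267 in each.
- 70/30 (68.6 and 29.4 deaths): means 1.585 and 1.038; power 0.354 and 0.178.

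**Probability that exactly one subset is significant.** The subsets contain different patients, so this is p₁(1 − p₂) + p₂(1 − p₁).
- 50/50: 2 × 0.267 × 0.733 = 39%. Both are significant in 7% and neither in 54%.
- 70/30: 0.354 × 0.822 + 0.178 × 0.646 = 41%.

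| True HR in both subsets | 50/50 | 60/40 | 70/30 | 80/20 | 90/10 |
|---|---|---|---|---|---|
| 0.75 | 28.3% | 28.4% | 28.7% | 29.3% | 30.1% |
| 0.682 | 39.2% | 39.5% | 40.6% | 42.3% | 44.7% |
| 0.65 | 43.9% | 44.4% | 46.0% | 48.6% | 52.0% |

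**No effect.** Exactly one significant: 2 × 0.05 × 0.95 = 9.5%. At least one: 1 − 0.95² = 9.75%.

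**Other level.** If the subsets were read at the one-sided 0.15 used to power OS, the HR 0.682 row would run from 47% to 59%.

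**Given a positive overall result.** By simulation at HR 0.682, among trials whose overall OS test reaches two-sided 0.05, exactly one subset is significant in 65% (50/50) to 74% (80/20).

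**Interaction test.** At two-sided 0.05 it falsely signals a platinum difference in 5% of trials with a uniform effect. The standard error of the log ratio of hazard ratios is √(4/d₁ + 4/d₂).
- 50/50: √(4/49 + 4/49) = 0.404. The ratio detectable with 80% power is exp[(1.960 + 0.842) × 0.404] = 3.1.
- 70/30: standard error 0.441, detectable ratio 3.4.

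**The case against.** The strongest reply is that the harm is inferred. Section 8.6 does not say that the two p-values will be compared or that a claim will be made for one platinum alone. Sections 6.1 and 8 place efficacy inference in the full ITT population, OS is secondary, and no boundary or success criterion uses the subsets. The shells already show both hazard ratios with 95% CIs, so a careful reader can see whether they overlap. All of this stands, and it limits the point to a supportive analysis.

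Two stronger readings are tempting and not supported. A reader might infer that about 40% of trials would mislead whatever the truth. That figure belongs to HR 0.682, 98 deaths, two-sided 0.05 and an assumed split. It also counts any pair of p-values on either side of 0.05, including 0.04 and 0.06 with nearly equal hazard ratios. A reader might also infer that Section 8.6 contradicts Section 5.4. Section 7.3 lists the baseline characteristics as height, weight, BMI, smoking history and ECOG status, while platinum choice is described as a stratification variable. At most, Section 5.4 lacks a cross-reference.

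It is also fair to say that an interaction p-value can be misread, since it will usually be non-significant at this size. That argues for reporting the estimate with its interval, not for leaving the term out.

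**Conclusion.** The point holds as a gap in a supportive analysis of a secondary endpoint. The plan tests treatment within each platinum subset but never tests or estimates whether the effect differs between them. Under a uniform effect at the design HR of 0.682, exactly one subset would be significant in about 39–45% of trials, against 5% false signals from an interaction test.

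That range assumes 98 deaths, two-sided 0.05 and a split between 50/50 and 90/10. The unknown split matters less than the true effect, which moves the figure from 28–30% (HR 0.75) to 44–52% (HR 0.65). Section 4 also allows the final OS analysis six months after the PFS analysis if that comes before 98 deaths. Fewer deaths would lower subset power and, at an even split and the design HR, lower the figure too.

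The primary PFS analysis and the overall OS analysis are unaffected.

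**What to change.** 1. In Section 8.6, add a treatment-by-platinum-choice term to the full-ITT OS Cox model and report the ratio of hazard ratios with its 95% CI and p-value.
2. Keep the subset hazard ratios and 95% CIs already in Tables 14.2.1.3 and 14.2.1.5, label them exploratory, and state that no platinum-specific conclusion will rest on the within-subset p-values.
3. Add a cross-reference to this analysis in Section 5.4.
4. Reconcile the shells, which define the subsets by platinum received, with the platinum choice of Section 8.6. The definition at the front of the SAP assigns the randomization-system entry to efficacy analyses with platinum choice as a model effect. The subset models have no such effect, so the rule does not settle which definition applies.

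The cost is one model term, a few lines of text and edits to two shells, with no change to data collection, sample size or the primary analysis. The downside is low power: 80% needs a ratio of hazard ratios of about 3.1 at a 50/50 split, so the text should say that a non-significant interaction does not show a uniform effect.
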